### **SECTION 3: SUBJECT POPULATION(S) (INDIVIDUALS/RECORDS/SPECIMENS)**

#### **1. Subjects To Be Enrolled on this UCI protocol (Persons/Records/Biospecimens)**

1. Complete the table of subject enrollments below. *Include additional rows for subject category/group, as needed.*
2. If the study involves the use of existing records or biological specimens, specify the maximum number to be reviewed/collected and the number needed to address the research question.

Category/Group (e.g., adults, controls, parents, children)	Age Range (e.g., 7-12, 13-17, adults)	Maximum Number to be Consented or Reviewed/Collected (include withdrawals and screen failures)	Number Expected to Complete the Study or Needed to Address the Research Question
Study Group	All ages	30	17
Control group (prospective controls)	All ages	30	17
Total: 60			

#### **3. Overall Study Sample Size**

If this is a multi-site study, provide the total number of subjects to be enrolled from all sites.

Not applicable: This study will only take place at UCI, and does not involve other sites.  
 Total number of subjects across all sites.

## A. SCREENING AND DETERMINING ELIGIBILITY

1. Indicate the **methods for obtaining information or biospecimens** for the **purpose of screening, recruiting, or determining eligibility** of prospective subjects. *Note: The screening activity is performed without the informed consent of the prospective subject or legally authorized representative (LAR).*
2. **UCI contact guidelines:**
  - a. *Directly communicate with the potential subject; do not leave a voicemail/message.*
  - b. *Only 5 attempts to contact the potential subject permitted.*
  - c. *Study team member contacting potential subject must be knowledgeable and able to answer questions related to the screening and the main study.*

Not applicable: Information and/or biospecimens will not be obtained for the purpose of screening, recruiting, or determining eligibility of prospective subjects. **Skip to Section 4.**

Study team will obtain information through **oral or written communication** with the prospective subject or LAR.

The recruitment script is an oral script and is actually written on the final page of this addendum. In order to avoid undue influence upon the subject, we will make it clear that participation in this study is completely voluntary, and that they may withdraw at any time.

Submit recruitment script for IRB approval. In addition to the minimum recruitment requirements, the recruitment script must include:

- ✓ *for telephone contact, the script must address when someone other than the potential subject answers the phone*
- ✓ *a description of the screening information and/or biospecimens that will be obtained*
- ✓ *the reasons for performing the screening tests*
- ✓ *what will happen to the information and/or biospecimens, if the potential subject is not eligible to participate in the study*

Study team will **screen medical records** to determine subject eligibility.

**Complete Appendix T to request a partial waiver of HIPAA Authorization.**

Study team will **screen non-medical records** (i.e., student records) to which they have access to determine subject eligibility. Specify: <Type here>

For research accessing student records, check here to confirm that evidence of FERPA compliance has been / will be obtained (and on file) from the local school/district site prior to the initiation of research.

Study team will **access stored identifiable biospecimens**.

3. For studies that will **screen medical records**, explain how the study team will access the clinical data. *Access to UCI Medical Center medical records for research purposes outside the capacity of the Honest Broker Services, such as access to physician notes, must be obtained from the Health Information Management Services.*

 34 CRF 99: *Family Educational Rights and Privacy Act (FERPA) applies to this research.*

Not applicable: This study does not involve the screening of medical records.

**How Obtained: Indicate all that apply:**

The study team will request specific patient information/data from UCIMC Health Information Management Services.

The study team will review their UCI patients' records and abstract data directly from those records.

The study team will request specific patient information/data from UCI Health Honest Broker Services. Describe the following:

Cohort selection criteria (e.g., use the available Clinical Terms from the Cohort Discovery Tool such as Demographics: Gender, Diagnoses: Asthma, Procedures: Operations on digestive system): [<Type here>](#)

Expected cohort size/patient count: [<Type here>](#)

Cohort attributes or data elements (e.g., lab test values, medication, etc.): [<Type here>](#)

The study team will review non-UCI Health records and abstract data directly from those records. Describe the following:

Specify the non-UCI Health records that will be screened: [<Type here>](#)

Explain how the study team has access to this clinical data: [<Type here>](#)

Other; explain: [<Type here>](#)

1. For studies that will screen existing biospecimens:

- a. Indicate the source of the specimens and explain how the existing specimens will be obtained.
- b. Indicate whether the specimens were originally collected for research purposes.

Not applicable: This study does not screen existing biological specimens.

**How Obtained: Indicate all that apply:**

UCI Health Pathology Biorepository

Other UCI-Health Entity; specify: [<Type here>](#)

Non-UCI Entity; specify: [<Type here>](#)

Other; explain: [<Type here>](#)

**Originally collected for research purposes:**

NO – Please explain: [<Type here>](#)

YES – UCI IRB approval granted under IRB protocol number (i.e. HS#): [<Type here>](#)

YES – Non-UCI IRB approval granted. Confirm one of the following:

A copy of the IRB Approval Notice and Consent Form for the original research collection will be submitted with the IRB application (APP). The IRB Approved Consent Form does not preclude the proposed activity.

A copy of the commercial Vendor Policy or a Letter from the Vendor attesting that the information was collected and will be shared in an appropriate and ethical manner will be submitted with the APP. The vendor's policy does not preclude the proposed activity.

5. Provide a complete list of the **data points, variables, and/or information** that will be collected **during the screening process** (i.e. data abstraction form). *Note: Only the minimum information necessary to determine subject eligibility should be collected during the screening process.*

For the experimental group, we would screen for the patient's age, type of lesion/diagnosis, location of the lesion, and the patient's willingness and ability to participate in the study.

For the control group, we would screen for the patient's age, type of lesion/diagnosis, location of the lesion, and the clearance of the lesion and response to treatment.

Check here if the list is submitted as a separate document with the application.

6. Specify what will happen to the information and/or biospecimens, if the potential subject is not eligible to participate in the study. *Note: Information or biospecimens of non-eligible subjects, may not be included as part of data analysis or disclosed beyond the study.*

The study team plans to destroy the identifiable information and/or biospecimens at the earliest opportunity consistent with conduct of the research. Describe the protocol specific plan and timeframe for destruction: [<Type here>](#)

The study team plans to retain the identifiable information and/or biospecimens. Describe protocol specific plan and provide rationale: If the patient does not want to participate in the study, but still wants to be treated with laser therapy, then we would offer them treatment without enrolling them in the study. This would involve collecting their information and performing necessary examinations in order to discern the optimal treatment, but their information, response to treatment, treatment methods, or any data pertaining to the patient would not be included in the study. The patient would simply be enrolled in our EHR as a patient and not a subject in this study.

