##### Inclusion Criteria

Subjects must meet the following criteria:

- Ability to understand and carry out subject instructions or be represented by a legally authorized guardian or representative
- All ages. Patients younger than 4 may have difficulty cooperating with the OCT measurements because each measurement requires the patient to remain still for approximately 30 seconds.
- Seeks and is scheduled for laser treatment of a skin lesion

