##### Exclusion Criteria

Any of the following will exclude participation in the study:

- Inability to understand and/or carry out instructions

If eligibility is based on age, gender, pregnancy/childbearing potential, social/ethnic group, or language spoken (e.g., English Speakers only), provide a scientific rationale.

Not applicable: Subject eligibility is not based on these factors.

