#### SECTION 4: RECRUITMENT METHODS

Check any of the following methods that will be used to recruit subjects for this study:

This study involves no direct contact with subjects (i.e., use of existing records, charts, specimens).

Specify database or IRB-approved protocol number (HS#), if applicable: <Type here>

Advertisements, flyers, brochures, email, Facebook, and/or other media.

Specify where recruitment materials will be posted: Recruitment emails may be sent out to the UC Irvine Campus through approved channels such as the SOM Dean's Office. We will also contact foundations with interest in this topic including The Sturge Weber Foundation and National Rosacea Society and will have then send email advertisements to their members and newsletter subscribers.

If subjects will be recruited by mail, e-mail, or phone, specify how their contact information will be obtained: Any subject recruited by email would be contacted through a general email list from those described above.

*Submit recruitment materials for IRB approval.*

The study will be listed on Clinicaltrials.gov. *All clinical research must be registered.*

The study will be listed on the UC Irvine Health Clinical Trials web page.

*Submit the UCIMC Standard Research Recruitment Advertisement for IRB approval.*

The UCI Social Sciences Human Subjects Lab/Sona Systems will be used.

*Submit the Social Science Human Subject Pool Recruitment Advertisement for IRB approval.*

Referral from colleagues

1. Study team will provide colleagues with UCI IRB-approved recruitment materials for distribution to potential subjects (e.g., recruitment flyer, introductory letter);
1. An IRB-approved recruitment letter will be sent by the treating physician. The letter will be signed by the treating physician and sent to his/her patients to inform them about how to contact study team members; and/or
2. Colleagues obtain permission from interested patient to release contact information to researchers.
3. Study team does not have access to patient names and addresses for mailing.
4. If colleagues will screen their patients' medical records to determine subject eligibility and approach patients directly about study participation: *Complete Appendix T to request a partial waiver of HIPAA Authorization.*

*Submit recruitment materials for IRB approval.*

Study team will contact potential subjects who *have given prior permission to be contacted* for research studies.

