Some subjects may be asked to participate in more than one imaging session. They will have the option of refusing participation in additional sessions. Follow-up examinations will be performed every 4 weeks. During these examinations, photography and imaging of the lesion of interest will be performed with optional laser treatments to be performed at the discretion of the treating physician and the patient. If no laser treatment is necessary, then the visit should take no more than 30 minutes for a quick follow-up and imaging. Additional laser treatment will require no more than 30 minutes to complete. The number of follow-ups is also determined at the discretion of the treating physician and the patient but could range from 1 to 6 depending on the response of the lesion to treatment.

Matched prospective controls will be gathered to be compared against the imaged, treated, experimental group. The prospective controls will be matched to age, gender, skin type, and type of skin lesion. They will be gathered via a retrospective chart review by abstracting and data directly from our own records.

Describe the duration of a subject's participation in the study. If there are sub-studies, include duration of participation in each sub-study.

For each visit: history and skin examination-30 minutes, imaging – up to 30 mins, and laser treatment – up to 30 mins. These are all maximums and will likely be shorter.

At a follow-up, the patient may or may not receive a laser treatment thus shortening the visit. A patient would be expected to have 1-6 follow ups depending on their response to treatment, so their maximum time in this study could range from about 1 to 6 months. Each follow-up visit is made about 4 weeks from the prior visit.

List data collection instruments (e.g., measures, questionnaires, interview questions, observational tool, etc.).

*Investigator-authored, non-standardized, or un-validated measures must be submitted for review.*

Standardized photography,  
OCT

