#### 4. Collection of Photographs, or Audio/Video Recording

Describe all procedures involving the use and/or collection of photographs, or audio/video recording.

Not applicable: This study does not involve photographs or audio/video recording. *Skip to Section 6.H.*

Once the essential information has been provided to the subject and the investigator is assured that an individual candidate understands the implications of participating in this study, the subject will be asked to give consent to participate in the study by signing an informed consent form.

Specify if photographs or audio/video recording will include subject identifiable information (e.g., name, facial image). If so, indicate which identifiers will be collected.

Subject will be asked to give consent to participate in the study by signing an informed consent form and photography release form. Patient identifying information such as name and, if needed, facial image will be collected only for the purposes of their patient records, however, when evaluating photographs for the study, their name will not be released or utilized, and their identifying facial information (eyes) will be hidden. Most photographs will not be subject identifiable.

Explain whether the photographs or audio/video recording will be included in subsequent presentations and/or publications and, if so, whether subject identifiers will be included.

Publications and/or presentations that result from this study will not include subject identifiable information.

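### Lesion location is recorded for both groups but not used in the design or analysis, so any body-site imbalance would stay in the primary comparison if site affects clearance

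*Combined protocol and SAP*

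**What the plan says.** Section 3, on screening and determining eligibility (item 5), lists the data to be collected. The list for the imaging group begins "For the experimental group, we would screen for the patient's age, type of lesion/diagnosis, location of the lesion". The list for controls covers age and then "type of lesion/diagnosis, location of the lesion, and the clearance of the lesion and response to treatment". Location is therefore available in both groups.

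No later rule uses it:

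- **Eligibility (Section 3).** The lesion criterion is "Seeks and is scheduled for laser treatment of a skin lesion", and the only exclusion is "Inability to understand and/or carry out instructions". Neither refers to body site.
- **Matching (Section 6, Research Procedures).** "The prospective controls will be matched to age, gender, skin type, and type of skin lesion". The controls are found by retrospective chart review of the team's own records.
- **Stratification (Section 6, Study Design).** Lesion type and lesion size are named, because they may influence response. Location is not.
- **Analysis (Section 6, Statistical Analysis Plan).** The primary comparison is a two-sample t-test at each treatment, without covariates. The items on further methods and on exploratory analyses are answered as not applicable.

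**The concern.** In a randomised trial, an unused baseline variable costs at most some precision. Here the groups are formed differently: one is enrolled prospectively and the other is picked from charts. Nothing in that process balances a variable that is not matched. Matching on lesion type helps only where type determines site. Eligibility admits any lesion at any site, so two patients with the same diagnosis can have lesions on different parts of the body.

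If clearance differs by site, a difference in site mix moves the group difference directly. It can create an apparent imaging benefit or hide a real one, and the unadjusted t-test has no means of separating the two. The information needed to deal with this is already on the screening list.

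**Working it through.** **Inputs from the documents (Sample Size Determination).** Mean clearance 60% vs 40%, so a difference of 20 points; SD 20; 17 per group; two-sided 5% test; 80% power.

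**Plan's own figure.** Standardised difference = 20/20 = 1.0. The exact t-test calculation gives 16.71 per group, rounded up to 17, with power 0.807 at 17. The stated sample size reproduces and is not in dispute.

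**Inputs that are assumptions.** Two site categories; a site effect of 10 to 20 clearance points; a difference in site share between groups of 20 to 30 percentage points. The documents give none of these.

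**Bias.** Bias = (difference in site share) × (site effect). The standard error of the group difference is 20 × √(2/17) = 6.86 points on 32 df. The false-positive rate is the noncentral t rejection probability when the only difference is the bias. The last column is power when the true difference is 20 and the imbalance works against imaging.

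| Site effect (points) | Imbalance (percentage points) | Bias (points) | False-positive rate | Power if against imaging |
|---|---|---|---|---|
| 10 | 20 | 0.2 × 10 = 2 | 5.9% | 0.72 |
| 10 | 30 | 0.3 × 10 = 3 | 7.1% | 0.67 |
| 20 | 20 | 0.2 × 20 = 4 | 8.7% | 0.62 |
| 20 | 30 | 0.3 × 20 = 6 | 13.6% | 0.51 |

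The table treats 20 as the SD within each group, site variation included. Simulation with 20 as the SD within each site (40,000 runs) gives slightly lower rates. Shares of 70% vs 40% give 6.9%, 9.4% and 12.3% for site effects of 10, 15 and 20 points; shares of 60% vs 40% with a 20-point effect give 8.0%. The upper end is therefore about 12% to 14%, depending on that convention.

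**Is such an imbalance plausible?** If a site is present in half the patients and both groups are independent draws, a gap of at least 4 patients (4/17 = 24 points) occurs in 23% of samples, and of at least 5 (5/17 = 29 points) in 12%. Chance alone would leave the t-test at 5% averaged over all samples. The rates above apply when an imbalance of that size is present, and selection from charts can make it systematic.

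**Cost and gain of adjusting.** In a linear model with group and one two-level site term (31 df), the standard error is SD × √(1 − R²) / √(8.5 × (1 − d²)). Here 8.5 = 34/4, R² is the share of variance explained by site, and d is the imbalance in site share, with overall site share near one half.

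- Balanced (d = 0), R² = 0.10: 20 × √0.90 / √8.5 = 6.51, power 0.845.
- Balanced, R² = 0.20: 20 × √0.80 / √8.5 = 6.14, power 0.884.
- d = 0.3, R² = 0.10: 18.97 / √(8.5 × 0.91) = 6.82, power about 0.81, essentially no gain.
- d = 0.3, R² = 0: 20 / √(8.5 × 0.91) = 7.19, power 0.77.
- Balanced, R² = 0: power 0.806, so the lost degree of freedom alone costs almost nothing.

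**The case against.** The strongest objection is that no passage says body site affects clearance. Study Design names lesion type and size as the factors that may matter, and the sample-size section attributes variation to lesion type, depth and vessel characteristics. Every bias figure is thus an assumed effect times an assumed imbalance. That stands: it limits what can be said about size, but it does not close the gap. It is also fair that lesion size has the better documentary claim to adjustment, since it is a named stratum that is neither matched nor in the t-test, and that 34 patients support few covariates.

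Three stronger readings are tempting, and the documents do not support them.

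- **That the plan meant to use location and forgot.** The screening form does say "Only the minimum information necessary to determine subject eligibility should be collected during the screening process", but this is the form's template instruction. The list beneath it does not track the design: gender, skin type and lesion size are design variables and are not on it. Research Procedures gives an ordinary reason to record location, namely documenting the skin area under study.
- **That recruitment makes a site imbalance likely.** Section 4 names "The Sturge Weber Foundation and National Rosacea Society" as e-mail routes. The documents do not say which body sites those memberships represent. Enrichment through them would be enrichment by diagnosis, which lesion-type matching largely absorbs. Subjects are also described as coming from the same institution's dermatology clinics.
- **That masking alters the grading of facial lesions.** The photography section says "their identifying facial information (eyes) will be hidden". This is a privacy step. Nothing says that the lesion is obscured or graded differently.

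**Conclusion.** The point holds in a conditional form. Location is recorded in both groups and used nowhere, and with non-randomised chart controls any site imbalance would stay in the primary comparison if site affects clearance. Under the assumed ranges the bias is about 2 to 6 points of the planned 20, and the false-positive rate reaches at most about 12% to 14%. If site has no effect on clearance, there is no bias.

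A reader might infer that the primary result will be biased, or that adjustment is a free gain in power. Neither follows. The documents contain no evidence on the direction or size of a site effect, and the gain to about 84% to 88% requires balanced groups with location explaining 10% to 20% of the variance. This is an inexpensive improvement to a pilot study's analysis, not a flaw that invalidates it.

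**What to change.** **Statistical Analysis Plan.** Prespecify one coarse two-level location grouping, fixed before outcomes are compared. Early fixing matters because control clearance is already seen at screening. Fit the grouping as a covariate with group in a linear model for the primary comparison, and report the unadjusted t-test alongside. State that location is kept in the analysis data set for enrolled subjects and controls, and tabulate it by group at baseline.

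**Research Procedures.** Where two control charts match a patient equally well, take the one at the same body site. A rigid fifth matching factor is not needed.

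**Cost.** Wording only; no new patients, visits or data items. Statistically, it costs one degree of freedom plus some precision if the groups are imbalanced and site does not matter (power about 0.77 instead of 0.81 at a 30-point imbalance). Two levels are about what 34 patients can support, so a finer site classification should not be attempted.

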### **2. Study Design**

Include an explanation of the study design (e.g., randomized placebo-controlled, cross-over, cross-sectional, longitudinal, etc.) and, if appropriate, describe stratification/ randomization/blinding scheme.

This is a longitudinal study with matched prospective controls. The patients will undergo treatment and follow-up over the course of 1-7 months. Their results will be compared to that of matched prospective controls with similar treatment and follow duration. There is no placebo, and patients will not be blinded.

Patients will be stratified based on their lesion type and the size of the lesion as these factors may impact the response to laser treatment and thus the data measurements from OCT. Photographs of the patients' treated lesions will be rated for lesion improvement by blinded physicians. OCT measurements of the lesion of interest will be used to validate the improvement and cosmetic results.

Provide precise definitions of the study endpoints and criteria for evaluation; if the primary outcomes are derived from several measurements (i.e., composite variables) or if endpoints are based composite variables, then describe precisely how the composite variables are derived.

Primary endpoints include photographic improvement of the lesion(s) of interest after 1 or more laser treatments. Two board certified dermatologists grade the degree of improvement (clearance of the lesion) in quartiles (no clearance=0-25, mild clearance=26-50, good clearance=51-75, excellent clearance=76-95, complete clearance=96-100). It will be up to the experienced treating dermatologist to determine the number of treatments necessary for maximum clearance of the lesion(s).

Secondary endpoints include measurements with OCT, which show reduced lesion thickness, lesion size, size of blood vessels, and density of blood vessels, and number of superficial blood vessels.

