### 3. Research Procedures

Provide a detailed chronological description of all research procedures.

A screening log of all potential subjects will be kept at our site. All screening evaluations must be reviewed by the investigator to establish patient eligibility prior to registering the patient for this study.

The following screening evaluation should be completed for all subjects on the first visit:

- Informed consent and photograph release form
- Focused medical history including diagnosis of lesion if applicable. This includes general questioning about the patient's health, well-being, allergies, and medications, and history of the skin lesion in question as identified by the patient and confirmed by the physician.
- Focused skin exam. This includes a detailed medical examination of the skin lesion in question.
- Documentation of area of skin to be studied. This will be determined by the patient's indication and confirmed by the physician.

On visit number one of the study, patients will consent to the study, and an area of skin to be studied will be photographed by digital photography. If the study area is on the face, subjects will be offered to protect their identity.

Non-invasive imaging will then be performed with OCT. Each individual scan with OCT takes about 30 seconds to complete, and we may perform multiple scans on larger lesions. Based on the data and information obtained, the appropriate laser device and settings will be applied for the most optimal treatment to achieve the best results with the fewest side effects. Then laser treatment will be performed on the lesion of interest. Immediate post-treatment imaging and photography will be conducted to assess the results of the treatment. This first visit should take no more than 1.5 hours: approximately 20 minutes for a medical history and focused skin examination, 30 minutes for imaging including photographs, and 30 minutes for laser treatment. These times are all maximums and will likely be shorter. The patient may take as long as needed to consent and is permitted to take the consent form home and return another day to sign and enroll.

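### The plan calls its controls prospective but gathers them by retrospective chart review; if charts are used, clearance is on the control screening list and no visible rule keeps it out of chart selection

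*Combined protocol and SAP*

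**What the plan says.** **Label.** Section 6, Study Design, states: "This is a longitudinal study with matched prospective controls". The same adjective is used for the controls in Section 1 (Purpose and Background), the enrolment table in Section 3, Research Procedures, the primary objective of the Statistical Analysis Plan, and the sample size paragraph.

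**Source.** Research Procedures says of these controls: "They will be gathered via a retrospective chart review by abstracting and data directly from our own records". The primary objective in the Statistical Analysis Plan likewise describes them as patients treated earlier in the conventional way, while still calling them a prospective control.

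**Screening data.** Section 3.A, item 5, asks for everything collected at screening and limits it to what eligibility requires. Both groups' lists begin with age, diagnosis and lesion location. The OCT group's list then adds willingness and ability to take part. The control list instead ends with "location of the lesion, and the clearance of the lesion and response to treatment".

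**Matching and follow-up.** "The prospective controls will be matched to age, gender, skin type, and type of skin lesion". Study Design adds: "Their results will be compared to that of matched prospective controls with similar treatment and follow duration". The number of treatments is left to the treating dermatologist's view of what clearance requires, and the number of follow-ups "could range from 1 to 6 depending on the response of the lesion to treatment".

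**Safeguards.** Photographs are rated by blinded physicians (Study Design). Research Procedures provides that "A screening log of all potential subjects will be kept at our site" and that the investigator reviews eligibility.

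**The concern.** The primary analysis is a between-group comparison without randomisation, so how the control group is formed decides how far a difference can be credited to OCT guidance. A concurrent control shares calendar time, operators, devices and photography with the OCT group. A historical one may not. The plan describes both.

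If the controls come from charts, their result already exists when they are chosen, and the screening list brings it into view. Should it influence which charts are kept, even unintentionally, the difference is distorted before any photograph is graded. Blinded grading would then measure a biased sample accurately, and the unadjusted two-sample t-test has no means of correcting it.

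**Working it through.** **1. The plan's own figure.** Inputs from Sample Size Determination: means 60% and 40%, SD 20%, two-sided 5%, 80% power, two-sample t-test. The normal approximation gives n = 2 × (1.960 + 0.842)² × (20/20)² = 15.7, so 16 per arm. The noncentral t gives 16.71, so 17 per arm, with power 80.7%. The stated 17 per arm reproduces and is not in dispute.

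**2. The sections side by side.**

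| Item | Where | On the control screening list? |
|---|---|---|
| Age, lesion type | matching factors, Research Procedures | yes |
| Gender, skin type | matching factors, Research Procedures | no |
| Clearance, response to treatment | outcome construct, Section 1 and Study Design | yes |

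The inclusion and exclusion criteria concern understanding and carrying out instructions (or being represented), age (all ages) and being scheduled for laser treatment. None uses clearance. So the list holds an item that neither eligibility nor matching needs, and lacks two that matching does need. Clearance can be known at screening only for someone already treated, so the list itself fits chart review better than concurrent enrolment.

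**3. How large could an effect be?** Illustration only. The selection strength, number of usable charts and split into matched sets are assumptions. From the plan: 17 per arm, SD 20, at most 30 controls consented or reviewed. Assume no true effect, and a selector who always takes the candidate with the lower score, where that score correlates ρ with graded clearance.

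In a matched set of two, the lower of two values lies on average 20/√π = 11.28 points below the mean. A set of one allows no choice. With m sets of two among 17, the expected false difference is ρ × (m/17) × 11.28.

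- 22 usable charts: five sets of two and twelve of one (5 × 2 + 12 = 22). 5/17 × 11.28 = 3.32.
- 30 usable charts, most biased matched split: thirteen sets of two and four of one (13 × 2 + 4 = 30). 13/17 × 11.28 = 8.63. This is the worst split because each further candidate in a set adds less, so an even spread gives the largest shift.
- 30 usable charts, uneven split: six sets of three, one of two, ten of one (18 + 2 + 10 = 30). The lowest of three lies 16.93 points below the mean on average. (6 × 16.93 + 11.28)/17 = 6.64.
- Upper bound without matching: lowest 17 of 30, expected shift 13.55.

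Rejection rates come from simulation (100,000 runs per case).

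| Scenario | False difference at ρ = 0.25 / 0.5 / 1 | Two-sided rejection |
|---|---|---|
| 22 charts, matched | 0.8 / 1.7 / 3.3 points | 5% / 5.5% / 7% |
| 30 charts, matched, uneven split | 1.7 / 3.3 / 6.6 | 5.5% / 7% / 15% |
| 30 charts, matched, most biased split | 2.2 / 4.3 / 8.6 | 6% / 9% / 25% |
| Lowest 17 of 30, no matching | 3.4 / 6.8 / 13.5 | 8% / 17% / 62% |

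At ρ = 0 rejection is 5% and power 81%. If selection ran the other way with a true 20-point effect, power in the most biased matched split would fall to 72% / 61% / 39%.

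**The case against.** **Clearance at screening may be innocent.** The form's prompt for item 5 itself mentions a data abstraction form, so the entry may be outcome abstraction written in the wrong field, or only a check that an outcome was recorded. A separate list or abstraction sheet may exist, some pages are not in the public copy, and most tick-box marks are lost. This stands: the claim can be only that no visible text provides the safeguard.

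**The listed item is not the endpoint.** A reader might infer that the primary endpoint itself is seen at screening. The documents do not support that. The endpoint is a photograph grade by two dermatologists, rated blind; the screening item is a chart-level record of the same construct. The two would be correlated to an unknown degree, and ρ = 1 is a limit, not an expectation.

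**Follow-up duration is not a stated selection rule.** The wish for similar treatment and follow-up reads as a comparability statement, and the explicit matching list omits it. The analysis compares groups at each treatment, and the sample size rests on one treatment. This is therefore a lesser point: only if charts were picked on treatment count or follow-up length would selection depend on response.

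**The figures can look larger than they should.** The 30 is a maximum that includes withdrawals and screen failures, so fewer charts may be usable, and every scenario assumes a selector who always leans one way. This also stands, which is why the 22-chart case belongs beside the others.

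**It is a pilot.** True, but the plan sizes a formal hypothesis test on this comparison, so the identity of the comparator still matters.

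**Conclusion.** The contradiction over the control group is certain and needs no assumption: the plan describes one group as both prospective and retrospectively gathered. It must be fixed, because the meaning of the primary comparison depends on it.

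The selection point is conditional on chart review. If controls are enrolled concurrently, no outcome exists at screening and the point falls away. If charts are used, the visible plan puts clearance before the person screening and sets no chart order, record window or concealment. Section 6 asks for the time frame of existing records, and no answer is visible. A reader might infer that controls will be chosen on their results, or that OCT will be favoured. Neither is supported: no text makes clearance a selection criterion, and the direction of any bias is unknown. With matching, the illustrated effect runs from negligible (0.8 points, 5% rejection) to serious (8.6 points, 25%), depending wholly on the assumptions above. This part is a cheap improvement, not a demonstrated flaw.

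**What to change.** 1. **Must fix.** Reconcile the sections and use one label throughout. If chart review is intended, call the controls historical in Sections 1, 3 and 6 and limit the conclusion accordingly. If controls are enrolled concurrently, correct the control screening list, Research Procedures and the primary objective of the Statistical Analysis Plan.
2. **If charts are used**, move clearance and response from the control screening list to outcome abstraction, and add gender and skin type. If needed, screen only for a yes/no answer on whether gradable photographs exist.
3. **If charts are used**, state a record window with a start date. Take consecutive eligible charts in date order, matched on the four stated factors, and say in advance which factor is relaxed first. Do not pick charts on number of treatments or length of follow-up. Record reviewed and rejected charts in the screening log and lock the list before outcomes are abstracted. Existing staff can do this.

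Cost: protocol wording and some extra chart handling. The 17 per arm stands, and no patient's treatment changes. The downsides are that a historical label weakens what can be concluded, and that 30 charts may not yield 17 close matches, hence the relaxation order.
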